5.8 Duration of Therapy

Patients will receive 2 cycles of protocol therapy prior to radiographic assessment for response or progression. Patients with clinical signs or symptoms of rapid disease progression prior to completing 2 cycles of protocol therapy may be removed from the study by the treating physician. Patients without disease progression at the time of response assessment will continue on the study, with repeat assessments after every 2 cycles (8 weeks +/- 7 days) until one of the criteria for treatment discontinuation is met. It is recommended that temozolamide treatment be discontinued after 1 year, due to risk of Myelodysplastic syndrome (MDS) . Patients can continue on Pazopanib. If patient is receiving benefit from combination treatment after one year, it is up to the treating physician's discretion whether or not the patient continues Temozolamide.

5.8.1 Criteria for discontinuing study treatment

When a patient is discontinued from treatment, the reason(s) for discontinuation will be documented on the appropriate eCRFs. Individual patients will continue on study therapy until any of the following occurs:

- 5.8.1.1** Unacceptable toxicity despite optimal supportive care and dose modifications (refer to Sections 5.6 and 5.7),
- 5.8.1.2** Disease progression by RECIST (version 1.1),
- 5.8.1.3** The patient or his/her legally authorized representative requests to discontinue protocol therapy or withdraws consent.
- 5.8.1.4** The decision is made by the treating physician to discontinue treatment due to one of the following:
 - 5.8.1.4.1** Patient non-compliance or lack of follow-up.
 - 5.8.1.4.2** Patient requires exclusionary concurrent treatment.
 - 5.8.1.4.3** Physician assessment that continuation of protocol therapy would be detrimental to the patient.

5.8.1.5 Death

5.8.2 Unacceptable toxicity

Patients must be removed from the study and protocol therapy discontinued for toxicities deemed by the treating investigator as unacceptable. These toxicities include but are not limited to:

- 5.8.2.2** Recurrent grade 3 or any grade 4 hemorrhage.
- 5.8.2.3** Gastrointestinal perforation requiring medical or surgical therapy.
- 5.8.2.4** Wound dehiscence requiring medical or surgical therapy.
- 5.8.2.5** Grade 4 hypertension despite optimal medical management
- 5.8.2.6** Grade 4 hypersensitivity reaction to either study drug, or Grade 3 reaction that recurs despite optimal supportive care.
- 5.8.2.7** Any Grade 3 or 4 toxicity that is deemed serious and/or life-threatening by the treating investigator after review with the Principal Investigator.
- 5.8.2.8** Any irreversible (lasting \geq 2 weeks despite optimal supportive care) Grade 3 or 4 toxicity (excluding nausea, vomiting, asymptomatic Grade 3 hypophosphatemia or Grade 3 hyponatremia, anemia, lymphopenia, or fatigue)
- 5.8.2.9** Any toxicity requiring treatment delay for $>$ 28 days or discontinuation of either study drug.

5.9 Follow-Up

After treatment discontinuation, patients will be followed every 6 months for 1 year in clinic and/or via phone for survival follow-up. The study will end 30 days after the last patient discontinues therapy and completes the protocol-defined follow-up period.

6.0 ENDPOINT ASSESSMENT

6.1 Phase I

6.1.1 Primary Endpoint

The primary objective for the phase I portion of this trial will be to determine the MTD of temozolomide and pazopanib combination in patients with advanced PNET. The primary endpoint will be toxicity, as assessed after 28 days of treatment (or completion of 1 cycle of therapy). Toxicity will be assessed at scheduled clinic follow up appointments every one to two weeks, as well as by investigator review of weekly laboratory testing; in the interim, toxicity may be assessed via patient contact with the study coordinator and/or clinical staff should new symptoms arise between visits. The MTD will be the level at which \leq 1 out of 6 patients experience a DLT (the highest dose level below the MAD). This will be the dose for the phase II portion of the study. Toxicity will be assessed according to the NCI CTCAE version 4.03.

6.1.2 Secondary Endpoints

6.1.2.1 Determine the safety and toxicity profile

One secondary objective for the phase I portion of this trial will be to determine safety and toxicity profile of the combination of temozolomide and pazopanib in this population. The endpoint for this objective will be toxicity, which will be assessed at scheduled clinic follow up appointments every one to two weeks, as well as by investigator review of weekly laboratory testing; in the interim, toxicity may be assessed via patient contact with the study coordinator and/or clinical staff should new symptoms arise between visits. Toxicity will be graded according to the NCI CTCAE version 4.03.

6.1.2.2 Describe the pharmacokinetics (PK) of the combination of temozolomide and pazopanib

Once the MTD is reached in the phase I portion of the study, this cohort will be expanded to include an 6 additional patients who will have PK studies performed. We will examine the effect of pazopanib on the pharmacokinetics of temozolomide. Full PK profiles will be taken after a single dose of temozolomide on Day 1 and again on Day 2 after administration of the combination of temozolomide and pazopanib. On Day 1, Cycle 1, the patient will have a time = 0 sample, take their dose of temozolomide, and then have samples drawn at the following times:

6.1.2.2.1 Day 1, Cycle 1

Time = 0 (prior to temozolomide dose) 10 min (+/- 5 minutes), 30 min (+/- 5 min), 1 hour (+/- 5 min), 2 hours(+/- 5 min), 3 hours(+/- 5 min), 4 hours (+/- 30 min) , 6 hours(+/- 30 min), 8 hours(+/- 30 min), and 24 hours(+/- 1 hour) post-dose.(drawn on Day 2.This will be the same sample as the pre-dose PK sample of Day 2 provided Day 2 drug administration is done within 1 hour of sample collection. One 3 ml sample is needed).

6.1.2.2.2 Day 2, Cycle 1

Time = 0 (prior to both pazopanib and temozolomide). This will be the same sample as the 24 hour post-dose PK sample of Day 1, provided Day 2 drug administration is done within 1 hour of sample collection. If this drug administration is delayed beyond one hour, then another 3 ml PK sample has to be collected for the pre-dose PK of Day 2), 10 min(+/- 5 minutes), 30 min(+/- 5 min), 1 hour(+/- 5 min), 2 hours(+/- 5 min), 3 hours(+/- 5 min), 4 hours(+/- 30 min), 6 hours(+/- 30 min), 8 hours(+/- 30 min), and 24 hours(+/- 1 hour) (done on Day 3) post dose.

Plasma temozolamide concentrations will be measured using our triple quadrupole API3000 LC-MS/MS after sample preparation by solid-phase extraction. The plasma temozolamide concentration versus time relationships will be modeled using the SAAM II software system (SAAM Institute, Seattle, WA) implemented on a Windows™-based PC as described by Argiris et al. Cmax and Tmax will be taken as the observed values.

These 6 patients in the PK cohort will be included in the phase II analysis. These patients will have correlative studies including MGMT. These 6 patients will be evaluated for phase II endpoints.

6.1.2.3 Observe the ORR

For all patients enrolled in the phase I portion of the study, we will describe the ORR as the best overall response recorded from the start of the study treatment until the end of treatment based on RECIST (version 1.1) criteria.

6.2 Phase II

6.2.1 Primary Endpoint

The primary objective for the phase II portion of this trial will be to determine the ORR. All enrolled patients will undergo contrast-enhanced CT or MRI imaging at baseline and after every 2 cycles of protocol therapy until study discontinuation. Patients will be assessed radiographically for response or progression after 2 cycles (8 weeks \pm 7 days) of study treatment. After 1 year of protocol therapy, patients may switch to imaging every 12 weeks (+/- 7 days) per treating physician discretion. Centralized RECIST measurements may be performed for some sites, depending upon feasibility. The schedule and methods of radiographic evaluation are described in Section 7.0.

6.2.2 Secondary Endpoints

6.2.2.1 Determine PFS, OS, DCR, and DOR.

For these endpoints, all enrolled patients will undergo contrast-enhanced CT or MRI imaging at baseline and after every 2 cycles of protocol therapy until study discontinuation. Please see Section 6.3 for definitions.

6.2.2.1.1 PFS will be defined as the time from the first study treatment to the first occurrence of progression or death.

6.2.2.1.2 OS will be defined as the time from first study treatment until death from any cause.

6.2.2.1.3 DCR will be defined as CR + PR +SD

6.2.2.1.4 DOR will be defined as the time from documented overall response to time of documented disease progression.

6.2.2.2 Determine the safety and toxicity profile of the combination in a larger cohort of patients.

All patients enrolled in the phase II portion of the trial will be evaluated for toxicity throughout the course of their participation on study and through 30 days after the last dose of study treatment.

6.2.3 Exploratory/Correlative Endpoints

Exploratory objectives of this study will look at different types of correlations. We will examine the relationship between tumor blood flow (as measured by perfusion functional computed tomography) and overall response. We will also correlate the expression of tissue MGMT as measured by immunohistochemistry with PFS.

6.2.3.1 Correlate the expression of tissue MGMT with PFS.

Immunohistochemistry for MGMT expression will be performed on all patients enrolled in the phase II portion of the study (the 6 patients in the PK cohort will also be included in these exploratory studies).

MGMT expression will be measured in a blinded fashion utilizing mouse monoclonal antibodies to MGMT. Nuclear MGMT will be scored as either present or absent in tumor cells and correlated with treatment outcome (PFS).

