1.6 Background and Rationale for Correlative Studies

1.6.1 O6-methylguanine DNA methyltransferase (MGMT) Expression

In this study we will examine the predictive role of MGMT expression in pancreatic NET to temozolomide therapy. O6-methylguanine DNA methyltransferase (MGMT) is a DNA repair enzyme believed to induce cancer cell resistance to O6-alkylating agents such as temozolomide. Inactivation of the MGMT gene by promoter methylation is associated with longer survival in patients with GBM treated with temozolomide.^{37, 38} Low MGMT expression, detected by immunohistochemistry (IHC), correlates with response to temozolomide treatment in low-grade oligodendrogloma, and MGMT immunostaining has been suggested as a marker for predicting tumor chemosensitivity.³⁹ MGMT promoter hypermethylation has been described in small groups of NET including pancreatic NET and carcinoid.⁴⁰ Ekeblad et al examined the role of MGMT expression in 27 patients with a variety of NET (12 PNET) treated with temozolomide monotherapy. They found a low percentage of MGMT-positive tumor cell nuclei in 43% of tumors. Four out of five patients with a radiologic response had tumors with low MGMT expressions. This suggests a possible predictive value of MGMT IHC in NET and needs to be further investigated.¹⁵

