9.3.1 Exploratory Study Statistical Analyses

9.3.1.1 MGMT expression

Changes in MGMT over time will be assessed using repeated measures analysis of variance; pre-treatment levels and changes in levels from baseline to day 30 will be related to response using a Wilcoxon rank sum test, and to PFS and OS using a proportional hazards regression model.

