12.2.2 Processing

For antigen retrieval, sections will be subjected to pretreatment with 45-min pressure boiling in citrate buffer (pH 6.0). Immunohistochemistry will be done using an autostainer (Dako Cytomation). Sections will be incubated with a mouse monoclonal MGMT antibody, diluted in antibody diluent (Dako Cytomation), at room temperature for 60 min. The reaction product will be revealed using Dako kit 50087 (Dako Cytomation). Sections will be counterstained with Mayer's hematoxylin. Initial experiments will be done with omission of the primary antibody. Nuclear MGMT will be scored as either present or absent in tumor cells and correlated with treatment outcome (PFS).

All staining and analysis will take place in the Pathology Core Facility at Northwestern University.

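### MGMT staining is scored present or absent with no threshold, while the cited evidence concerns a low percentage of positive nuclei and the analysis section refers to levels (minor; exploratory endpoint)

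*Combined protocol and SAP*

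**What the plan says.** **Scoring.** Section 6.2.3.1 states the rule, "Nuclear MGMT will be scored as either present or absent in tumor cells and correlated with treatment outcome (PFS", and says MGMT is measured blinded. Section 12.2.2, the laboratory section, has the same rule: "Nuclear MGMT will be scored as either present or absent in tumor cells". Neither section mentions a percentage of positive nuclei, an intensity scale or a cut-off.

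**Rationale.** Section 1.6.1 cites promoter methylation in glioblastoma and hypermethylation in small groups of NET. Its immunohistochemistry evidence is about low expression. In oligodendroglioma, "Low MGMT expression, detected by immunohistochemistry (IHC), correlates with response to temozolomide treatment". In a series of 27 NET patients (12 PNET) on temozolomide alone, "They found a low percentage of MGMT-positive tumor cell nuclei in 43% of tumors", and "Four out of five patients with a radiologic response had tumors with low MGMT expressions". The protocol's own conclusion is cautious: "This suggests a possible predictive value of MGMT IHC in NET and needs to be further investigated".

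**Analysis.** Section 9.3.1.1 says that "pre-treatment levels and changes in levels from baseline to day 30 will be related to response using a Wilcoxon rank sum test", with proportional hazards regression for PFS and OS.

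**Objective.** Section 2.2.3.1 is the only exploratory objective still listed: to correlate MGMT by immunohistochemistry with ORR and PFS. At most 27 patients contribute (9.2.1).

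**The concern.** The three parts of the plan describe different variables. The rationale uses a graded measure, with the favourable group at the low end. The scoring sections record a yes/no value. The analysis section uses levels, and no section says how a level is obtained.

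On the plain reading of the scoring rule, any positive nuclei make a tumour present. A tumour with a few positive nuclei, which the rationale would place in the favourable group, is then pooled with a tumour that is almost wholly positive. The absent group shrinks and the present group becomes a mixture, so any real association between low expression and outcome is diluted.

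What is at stake is how informative the correlative result can be. Tissue is required from every PK-cohort and phase II patient (Table 10, footnote 15), and a yes/no score cannot later be expanded to a percentage without re-reading the slides.

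**Working it through.** The plan gives no sample size, power or effect size for MGMT, so there is no figure to reproduce for this endpoint. The only design figure used is the maximum of 27. The Simon design it comes from (2/11, 7/27, 19% v 39%) does reproduce by exact binomial: early stopping under 19% is 65.1% (stated 65%), power 80.8% (stated 80%) and type I error 0.099 (limit 0.10).

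**Inputs from the documents**
- n = 27 (9.2.1).
- Share of low expressers: 43%, borrowed from the cited NET series (1.6.1).
- Overall response of 39%, the design alternative (9.2.1), used to anchor the assumed response rates.

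**Assumptions, not in the documents**
- q = share of low expressers with no positive nuclei, varied over 100%, 75%, 50% and 25%.
- Response 60% in low and 23% in other tumours: 0.43 × 0.60 + 0.57 × 0.23 = 0.389.
- A milder split of 50% v 31%: 0.43 × 0.50 + 0.57 × 0.31 = 0.392.
- Two-sided Fisher test at 0.10.

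**Formulas**
- Expected absent group = 27 × 0.43 × q.
- Low expressers as a share of the present group = 0.43(1 − q) / (1 − 0.43q).
- Response in the present group = [0.43(1 − q) × p_low + 0.57 × p_other] / (1 − 0.43q).

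Example at q = 50%, 60% v 23%:
- Absent group: 27 × 0.43 × 0.5 = 5.8 patients.
- Low share of the present group: 0.215 / 0.785 = 27%.
- Response in the present group: (0.215 × 0.60 + 0.57 × 0.23) / 0.785 = 33.1%.
- Difference: 60 − 33.1 = 27 points, against 60 − 23 = 37 points for low v not-low.

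**Response: power of the absent v present comparison** (20,000 simulated trials per row)

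| q | Expected absent group | Low share of present group | Difference, 60 v 23 | Power, 60 v 23 | Power, 50 v 31 |
|---|---|---|---|---|---|
| 100% | 11.6 | 0% | 37 points | 52% | 18% |
| 75% | 8.7 | 16% | 31 points | 36% | 14% |
| 50% | 5.8 | 27% | 27 points | 23% | 10% |
| 25% | 2.9 | 36% | 24 points | 12% | 6% |

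The q = 100% row is also the power of a low/not-low split, because the two scorings then coincide. Repeat runs agree to about one percentage point.

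**PFS.** Same n and share of low expressers, exponential times, every patient with an event (best case), two-sided 5% log-rank test, 4,000 simulated trials per cell. The hazard ratios (low v other) are assumed.

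| Hazard ratio | Low v not-low | Absent v present, q = 75% | q = 50% | q = 25% |
|---|---|---|---|---|
| 0.3 | 79% | 46% | 25% | 11% |
| 0.4 | 57% | 33% | 18% | 10% |
| 0.5 | 38% | 23% | 14% | 9% |

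The pattern matches response. The benchmark in both tables is a low/not-low split. A rank analysis of the percentage itself was not simulated, because that needs a distribution of percentages that the documents do not give.

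**The case against.** Much of the case on the other side stands and limits the point.

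- **The rationale is mixed and hedged.** Section 1.6.1 also cites promoter silencing, which a present/absent score fits reasonably well. Its NET evidence is five responders in a mixed series. If response were unrelated to MGMT, four or more of five would be low with probability 5 × 0.43⁴ × 0.57 + 0.43⁵ = 0.11. The protocol claims only a possible predictive value.
- **The loss rests on unknown inputs.** If every low expresser has no staining, the two scorings are identical. If the effect is mild, power is about 18% even with a perfect low/not-low score. A reader might infer that this scoring rule would make the trial miss a real association. The documents do not support that: a null result would be likely under either scoring unless the effect is large.
- **The planned tests do run.** A reader might infer that a yes/no value cannot enter the rank sum test. It can: with ties, the test in effect compares two proportions, and a proportional hazards model accepts a binary covariate. What remains is that 9.3.1.1 speaks of levels that no section defines.
- **The wording is ambiguous.** Present or absent in tumour cells could be read cell by cell, which would allow a percentage. This does not rescue the rule, because no section says how cell-level calls become a tumour-level value. It does mean that a cut at zero is the plain reading, not a settled one.
- **No arm is affected.** Phase II is single-arm, so misgrouped tumours enter a comparison category, not a treatment arm, and no treatment choice follows from the score.

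**Conclusion.** The mismatch is real. The scoring rule in 6.2.3.1 and 12.2.2 matches neither the percentage-based evidence in 1.6.1 nor the levels analysed in 9.3.1.1, and on its plain reading it may dilute the association of interest. The loss ranges from nothing (all low expressers unstained) to a fall in power from about 52% to 12% for response (a quarter of them unstained). That range assumes 27 patients, 43% low, 60% v 23% response and a two-sided Fisher test at 0.10. With 50% v 31%, power is 18% at best.

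The point is minor. The endpoint is exploratory, and the MTD, the Simon decision and the safety analyses do not depend on it. It is worth acting on because the better measure costs little and loses nothing, not because the stated rule can be shown to spoil the result.

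**What to change.** In 6.2.3.1 and 12.2.2, have the same blinded slide reader record the percentage of MGMT-positive tumour nuclei on the same slides. In 9.3.1.1, name the baseline percentage as the predictor, with the rank sum test for response and proportional hazards regression for PFS and OS. Keep present/absent as a secondary summary derived from the percentage, and state its threshold. Analysing the percentage directly avoids having to choose a low/high cut-off.

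The cost is wording in three sections and one more field on the pathology form; slides, stain and slide reader are unchanged. The downside is slightly more reading time and more variation between reads than with a yes/no call.

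This does not resolve the planned change from baseline to day 30 in 9.3.1.1. Footnote 16 of Table 10 rules out a repeat biopsy for correlative studies, so that is a separate inconsistency; the proposal here needs only the baseline value.

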6.3 Definitions

Target and non-target lesions will be defined by RECIST guidelines (version 1.1).

6.3.1 Measureable disease

Measurable lesions are defined as measurable in at least one dimension with clearly defined margins; at least one diameter must be greater than 0.5 cm. Bone lesions are excluded.

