3.2 Inclusion Criteria

3.2.1 Patients must have histologically confirmed well –differentiated islet cell carcinoma (PNET) not amenable to surgical resection.

3.2.2 Patients must be age 18 years or older.

- 3.2.3** Patients may have had 0-4 prior therapies.
 - 3.2.3.1** Prior chemoembolization or local ablative therapies are permitted if completed \geq 6 weeks prior to study enrollment.
 - 3.2.3.2** Prior temozolomide is permitted.
- 3.2.4** Patients must have an ECOG performance status \leq 2 (refer to Appendix I).
- 3.2.5** Patients must have a life expectancy $>$ 3 months.
- 3.2.6** Patients must have radiographically measurable disease as defined by RECIST version 1.1 criteria.
- 3.2.7** Patients' baseline blood pressure must be adequately controlled with or without antihypertensive medications prior to enrollment (systolic $<$ 140 mmHg, diastolic $<$ 90 mmHg).
- 3.2.8** Patients must have LVEF \geq 50 as measured by echocardiogram or MUGA.
- 3.2.9** Patients must have adequate baseline organ and marrow function as defined below:
 - 3.2.9.1** Absolute neutrophil count (ANC) \geq 1,500/ μ L
 - 3.2.9.2** Platelets \geq 100,000/ μ L
 - 3.2.9.3** Hemoglobin \geq 9.0 g/dL
 - 3.2.9.4** Total bilirubin \leq 2 mg/dL or \leq 1.5 times upper limit of normal (ULN)
 - 3.2.9.5** AST (SGOT) and ALT (SGPT) \leq 2.5 times ULN
 - 3.2.9.6** INR \leq 1.2 times ULN. Subjects receiving anticoagulant therapy are eligible if their INR is stable and within the recommended range for the desired level of anticoagulation.
 - 3.2.9.7** Activated partial thromboplastin time (aPTT) \leq 1.2 x ULN
 - 3.2.9.8** Albumin \geq 2.8 g/dL
 - 3.2.9.9** Serum creatinine \leq 1.5 times ULN OR if serum creatinine \geq 1.5 mg/dL, calculated creatinine clearance \geq 30 mL/min
 - 3.2.9.10** Urine protein to creatinine ratio $<$ 1 OR 24-hour urine protein $<$ 1 g
- 3.2.10** Patients must be able to tolerate oral medications.
- 3.2.11** Females of child-bearing potential must have a negative pregnancy test within 14 days of study enrollment and must agree to use an effective method of birth control during treatment and for three months after receiving their last dose of study drug. Males must agree to use an effective method of birth control during treatment and for three months after receiving their last dose of study drug. All patients must notify treating provider immediately if any suspicion of pregnancy or conception.

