6.3.3 Target lesions

All measurable lesions up to a maximum of 2 lesions per organ and 5 lesions in total, representative of all involved organs should be identified as target lesions and recorded and measured at baseline. Target lesions should be selected on the basis of their size (lesions with the longest diameter) and their suitability for accurate repeated measurements (either by imaging techniques or clinically). A sum of the longest diameter (LD) for all target lesions will be calculated and reported as the baseline sum diameters. The baseline sum diameters will be used as reference by which

to characterize the objective tumor. Pathological lymph nodes: nodes with a short axis of ≥ 15 mm are considered measurable and assessable as target lesions. The short axis measurement should be included in the sum of lesions in calculation of tumor response. Nodes that shrink to < 10 mm short axis are considered normal.

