6.4 Evaluation of response to therapy

The following criteria (RECIST version 1.1) will be used to define disease response to therapy based upon radiographic measurements using contrast-enhanced CT or MRI imaging with contiguous cuts of 10 mm or less in slice thickness:⁴¹

Table 8: Definitions & Evaluation of Response

Evaluation of Target Lesions	
Complete Response (CR)	Disappearance of all target lesions.
Partial Response (PR)	At least a 30% decrease in the sum of diameters of target lesions, taking as reference the baseline sum diameters.
Progressive Disease (PD)	At least a 20% increase in the sum of diameters of target lesions, taking as reference the smallest sum recorded on study AND an absolute increase in the sum of at least 5 mm OR the appearance of one or more new lesions.
Stable Disease (SD)	Neither sufficient shrinkage to qualify for PR nor sufficient increase to qualify for PD, taking as reference the smallest sum of diameters while on study
Evaluation of Non-Target Lesions	
Complete Response (CR)	Disappearance of all non-target lesions and normalization of tumor marker level.
Incomplete Response/ Stable Disease (SD)	Persistence of one or more non-target lesion(s) or/and maintenance of tumor marker level above the normal limits.
Progressive Disease (PD)	Appearance of one or more new lesions and/or unequivocal ¹ progression of existing non-target lesions ² .

¹ For unequivocal progression on the basis of non-target disease, there must be an overall level of substantial worsening in non-target disease such that, even in presence of SD or PR in target disease, the overall tumor burden has increased sufficiently to merit discontinuation of therapy. The designation of overall

progression solely on the basis of change in non-target disease in the face of SD or PR of target disease will be extremely rare.⁴²

²In the uncommon scenario of a mixed response with response or stable disease in target lesion(s) but progression in non-target lesions only, assessment of overall response will be made by the treating investigator and confirmed with the Principal Investigator and DMC.

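### Section 6.3.1 gives measurable lesions a 0.5 cm floor beside the protocol's RECIST 1.1 rule, so two definitions feed the primary response count; the effect on the trial is probably small

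*Combined protocol and SAP*

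**What the plan says.** Eligibility is set in section 3.2.6: "Patients must have radiographically measurable disease as defined by RECIST version 1.1 criteria". Section 6.3 says that target and non-target lesions follow the same guideline. Neither place prints a minimum size.

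Section 6.3.1 then gives its own definition. A lesion is measurable if it can be measured in one dimension, has clear margins and passes a size test: "at least one diameter must be greater than 0.5 cm". The one exclusion is "Bone lesions are excluded". Section 6.3.2 puts small lesions among the non-measurable ones without saying what counts as small.

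Three other rules bear on this floor:

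- Section 6.3.3 treats nodes separately: "nodes with a short axis of ≥ 15 mm are considered measurable and assessable as target lesions", and "Nodes that shrink to < 10 mm short axis are considered normal".
- Section 6.4 allows "contiguous cuts of 10 mm or less in slice thickness".
- Table 8 grants partial response (PR) at a 30% fall in the sum of target diameters, with no minimum change in millimetres. Progression by target growth needs a 20% rise and also at least 5 mm.

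The primary phase II endpoint is the count of complete and partial responses. Section 9.2.1 stops at 2 or fewer of 11 and calls the combination active at 8 or more of 27.

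**The concern.** A site choosing target lesions can follow the guideline named in 3.2.6 and 6.3 or the number printed in 6.3.1, and nothing says which governs. A site that uses the printed number may take as a target a lesion smaller than one permitted slice. Read alone, 6.3.1 also admits a node of 6 to 14 mm that 6.3.3 would not accept.

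Response is judged on a relative change. The smaller the target sum, the fewer millimetres of reading error are needed to cross the PR threshold. Such errors add responses to the primary count, and the attained type I error has almost no room below its 0.10 limit. Central measurement is optional under section 6.2.1.

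**Working it through.** **1. The plan's own design.** Inputs from section 9.2.1: response rates of 19% (null) and 39% (alternative), 11 patients in stage 1 and 16 more in stage 2, stop at 2 or fewer, declare activity at 8 or more of 27.

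- Early stopping = P(X1 ≤ 2), X1 ~ Bin(11, p).
- Declaring activity = Σ over x = 3 to 11 of P(X1 = x) · P(X2 ≥ 8 − x), X2 ~ Bin(16, p).
- At p = 0.19: early stopping 0.651, type I error 0.0993. At p = 0.39: power 0.808.

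The stated 65%, 0.10 and 80% are reproduced.

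**2. Millimetres needed for PR on a lone target.** 0.30 × 6 = 1.8 mm; 0.30 × 10 = 3.0 mm; 0.30 × 20 = 6.0 mm.

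**3. False PR with no true change.** The documents give no reading error, so an SD of 1.0 to 2.0 mm per lesion measurement is assumed: normal, independent, on the baseline and on three follow-up scans. PR is a follow-up sum ≤ 0.7 × the baseline sum. It is confirmed if met on two consecutive scans; the 8-week imaging interval satisfies the 4-week minimum in section 6.6.

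| Targets | Confirmed false PR, SD 1.0 mm | SD 2.0 mm |
|---|---|---|
| One of 6 mm, all baselines kept | 2.2% | 13% |
| One of 6 mm, measured baseline above 5 mm | 2.6% | 18.6% |
| One of 10 mm | 0.1% | 4.4% |
| One of 20 mm | about 0 | at most 0.1% |
| 20 mm and 6 mm together | 0 | 0.15% |
| Five of 6 mm | about 0 | 1.3% |

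The second row discards simulated baselines of 5 mm or less, because 6.3.1 would not call those lesions measurable. This selects baselines that were read too large, so the rate rises. Without confirmation, the lone 6 mm figures are 17-47% (all baselines) and 21-62% (baseline above 5 mm).

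**4. Effect on the trial.** Let s be the share of patients whose only target is about 6 mm and q their false-PR probability. Assume no false responses in other patients and a true response rate of 19% throughout. The observed rate is p = 0.19 + 0.81 · s · q. The documents do not give s; take s = 5% for illustration.

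- q = 3%: p = 0.19 + 0.81 × 0.05 × 0.03 = 0.1912; type I error 0.102.
- q = 19%: p = 0.19 + 0.81 × 0.05 × 0.19 = 0.1977; type I error 0.118.

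These use the higher range, conditioned on the measured baseline. With q = 13%, p = 0.1953 and the type I error is 0.112.

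**The case against.** Several stronger readings are tempting, and the documents do not support them.

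- *The 0.5 cm floor contradicts a RECIST 1.1 number.* The protocol names that guideline but does not print its minimum for non-nodal lesions. What the text shows is two definitions with no rule of precedence.
- *The slice and node limits contradict 6.3.1 outright.* Section 6.4 sets a maximum thickness, so thinner cuts are allowed. Section 6.3.3 gives nodes their own rule, and a normal-node limit says nothing about a non-nodal deposit. These are incompatibilities left by the missing cross-references.
- *Patients with only 6-9 mm disease can be enrolled.* Eligibility rests on 3.2.6, which cites RECIST 1.1 and not 6.3.1, and section 3.4 forbids waivers. This would happen only if a site applied 6.3.1 instead.
- *Type I error rises to 0.153.* That is the value at a null rate of 21%. To get there from 19%, s · q must equal 0.02 / 0.81 = 0.0247, so s would be about 82% at q = 3% or 13% at q = 19%. Nothing in the documents suggests such a share.
- *The floor is what makes progression hard to reach.* A lone 6 mm target does need 5/6 = 83% growth, but the 5 mm minimum governs any sum below 25 mm; a lone 10 mm target needs 50%. New lesions and non-target progression still count.

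The best defence is practical. Section 6.3.3 selects the largest lesions suited to repeat measurement, up to five. Section 6.6 asks for confirmation, with review by the principal investigator and the DMC. With a larger target present, the false-response rate is near zero. That argument limits the size of the problem but does not settle which definition applies. The safeguards also have gaps: 6.3.3 wants all involved organs represented, and 6.6 lets unconfirmed responses be reported as such where confirmation is not feasible.

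**Conclusion.** The point stands as a defect in a definition that feeds the primary endpoint. Section 6.3.1 and the RECIST 1.1 references in 3.2.6 and 6.3 are both operative. The printed floor is below the permitted slice thickness and has no exception for the node rule.

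The consequence is confined to patients with only sub-centimetre targets. For a lone unchanged 6 mm lesion, false confirmed PR is about 2-13%, or 3-19% given a measured baseline above 5 mm, against 0.1-4% at 10 mm. These ranges rest on the assumed SD of 1 to 2 mm and on independent errors. At trial level the effect is probably small: type I error of about 0.102-0.118 if 5% of patients had such a target, against 0.099. That 5% is an illustration, and the documents do not show that any such patient exists. The sample size and decision boundaries are not in error.

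**What to change.** Delete the 0.5 cm clause from 6.3.1. Define measurable lesions by the RECIST 1.1 criteria that 3.2.6 and 6.3 already require, and as no smaller than the slice thickness used for that patient. Add a cross-reference to the node rule in 6.3.3.

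Before the stage 1 count, check the baseline target lists of enrolled patients. Keep every enrolled patient in the intent-to-treat denominator of section 9.2.2, re-derive response from qualifying targets only, and report any patient who has none.

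The cost is a short amendment and a review of the baseline lists. Some lesions may move to non-target status, and a patient with only sub-centimetre targets would stay in the denominator but could not count as a responder.
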